7.5.3 VISIT 3: ASSESSMENT OF PAIR # 2 AND STUDY EXIT

This visit will occur 6-10 days after dispense of lens pair #2.

Procedures for assessment of pair # 2 will be followed (similar to assessment of pair # 1) as detailed in the follow up visit section 7.5.2.

- Participant will also rate their overall preference between lens pair #1, lens pair-#2 or no preference (and reason for preference) for a number of considerations that include:
 - Overall comfort preference, and reason for preference.
 - Overall vision preference, and reason for preference.

- The lenses will be removed by the participant and retained in the CCLR (see section 7.4.6 for disposing consumables).
- Slit lamp biomicroscopy assessment will be conducted according to the CVI approved study biomicroscopy CRF, using sodium fluorescein dye.
- Exit visual acuity will be performed with habitual glasses.
- The participant will be discharged and will sign the study completion forms.

7.5.4 SUMMARY OF VISITS AND PROCEDURES

Table 3 summarizes the visits and procedures for the study.

Table 3: Summary of Visits and Procedures

	Visit 1 Screening / Baseline & Dispensing lens pair #1	Visit 2 Follow-up of lens pair #1/ Dispensing lens pair #2	Visit 3 Follow-up of lens pair #2 and Exit
Informed Consent	✓		
Meet inclusion/exclusion criteria	✓		
History at baseline	✓		
Demographics	✓		
VA with spectacles or refraction	✓		✓

	Visit 1 Screening / Baseline & Dispensing lens pair #1	Visit 2 Follow-up of lens pair #1/ Dispensing lens pair #2	Visit 3 Follow-up of lens pair #2 and Exit
Auto-refraction & keratometry	✓		
Sphero-cylindrical refraction	✓		
Best corrected (sphero-cyl) VA monocular and binocular	✓		
Best corrected sphere	✓		
Biomicroscopy	✓	✓	✓
[REDACTED]		█	█
Symptoms & problems	✓	✓	✓
[REDACTED]	█		
Dispense new lenses	✓	✓	
Participant ratings (at scheduled visit)	✓	✓	✓
Surface assessments	✓	✓	✓
[REDACTED]	█	█	█
Over Refraction	✓	✓	
VA with contact lenses	✓	✓	✓
Assessment of adverse events	✓	✓	✓
Exit study			✓

8 MONITORING PROTOCOL ADHERENCE

Adherence to study visit windows, lens wearing schedule, and time windows around other data collection points (i.e. subjective ratings) will be monitored internally by the CCLR and reported as deviations from the windows described in the protocol in the weekly reports and study report.

9 ADVERSE EVENT REPORTING

9.1 ADVERSE EVENT DEFINITIONS

An 'adverse event' refers to any undesirable clinical occurrence in a participant, whether it is considered to be device-related or not. Adverse events (AE) may be classified as 'unanticipated adverse device effects,' 'serious adverse events,' 'significant adverse events,' or 'non-significant adverse events,' as defined below.

A number of conditions may result in temporary discontinuation until resolution. These include corneal infiltrates, corneal staining, limbal injection, bulbar injection or bulbar and tarsal conjunctival abnormalities.

See SOP012_v01_Adverse Event Management and Reporting for a description of adverse events, including management and reporting.

Classification	Definition
Serious Adverse Event	Those events that are life-threatening, or result in permanent impairment of a body function, or permanent damage to a body structure or necessitate medical (therapeutic) or surgical intervention to preclude permanent impairment of a body function or permanent damage to a body structure.
Significant Adverse Event	Those non-serious adverse events that occur with contact lens usage that are not sight-threatening but are usually symptomatic and may warrant therapeutic management and /or temporary or permanent discontinuation of contact lens wear.
Non-Significant Adverse Events	Those less severe non-serious adverse events that occur with contact lens usage that are not sight-threatening, may or may not be symptomatic and may warrant palliative management, such as ocular lubricants or temporary interruption of contact lens wear.
Unanticipated Adverse Device Effect	Adverse events in a clinical trial that were not previously identified in the protocol in terms of nature, severity, or degree of incidence. An Unanticipated Serious Adverse Device Effect is an unanticipated adverse event that is serious in nature and caused by or associated with the device and is considered reportable.

AE classification, coding (for reporting to the sponsor) and examples are provided in the following table of Contact Lens Adverse Event Classification and Reporting table:

Code	Condition	Reporting
Serious Adverse Events		
01	Presumed infectious keratitis or infectious corneal ulcer	Notify sponsor as soon as possible, within 24 hours ; IRB reporting as per requirements
02	Permanent loss of \geq 2 lines of best spectacle corrected visual acuity (BSCVA)	
03	Corneal injury that results in permanent opacification within central cornea (6mm)	
04	Uveitis or Iritis (e.g. presence of anterior segment inflammation as described in ISO 11980, Annex B)	
05	Endophthalmitis	
06	Hyphema	
07	Hypopyon	

08	Neovascularization within the central 6mm of cornea	
00	Other serious event	

Significant Adverse Events

11	Peripheral (outside central 6mm), non-progressive, non-infectious ulcer	Notify sponsor as soon as possible, within 5 working days ; IRB reporting as per requirements
12	Symptomatic corneal infiltrative event	
13	Superior epithelial arcuate lesions (SEALs) involving epithelial split	
14	Corneal staining \geq dense coalescent staining up to 2mm in diameter (e.g. moderate, ISO 11980 grade 3)	
15	Corneal neovascularization \geq 1.0mm vessel penetration (e.g. \geq ISO 11980 Grade 2), if 2 grade change from baseline	
16	Any temporary loss of \geq 2 lines BSCVA for \geq 2wks	
17	Any sign and/or symptom for which participant is administered therapeutic treatment or which necessitates discontinuation of lens wear for \geq 2 weeks	
10	Other significant event	

Non-significant Adverse Events

21	Conjunctivitis (bacterial, viral or allergic)	Notify sponsor as soon as possible, within 5 working days ; IRB reporting as per requirements
22	Papillary conjunctivitis if \geq mild scattered papillae/follicles approximately 1mm in diameter (e.g. ISO 11890 Grade 2), if 2 grade change from baseline	
23	Asymptomatic corneal infiltrative events	
24	Any sign and/or symptom for which temporary lens discontinuation for $>$ 1 day is recommended (if not already classified)	
20	Other sign and/or symptom warranting classification as a non-significant adverse event	

9.1.1 NORMAL OR ADAPTIVE SYMPTOMS

Transient symptoms such as end-of-day dryness, lens awareness, itching or burning or other discomfort may occur with contact lens wear and may occasionally reduce wearing time. These are not reported as adverse events unless in the investigator's opinion they are unexpected in nature, severe or have a high rate of occurrence.

9.2 PROCEDURES FOR ADVERSE EVENTS

Treatment of an adverse event will depend on its nature and severity. Based on the clinical judgment of the investigator the participant may be referred to an ophthalmologist for treatment. The investigator will attempt to determine whether the reaction is related to the test device or a result of other factors. An adverse event form (Appendix 6) will be completed for each adverse event. If both eyes are involved, a separate adverse event form will be completed *for each eye*. Whenever possible, the adverse event will be photo-documented.

Expenses incurred for medical treatment as part of study participation will be paid by the sponsor (bills and prescription receipts kept). The participant must be followed until resolution or no further change is anticipated and/or referred for further care with the appropriate health care professional and/or recorded as being under appropriate health care as per investigator's discretion. A written report will be completed indicating the subsequent treatment and resolution of the condition.

9.3 REPORTING ADVERSE EVENTS

All potential Serious and Unanticipated Adverse Device Effects that are related or possibly related to participant's participation will be reported to the Principal Investigator and the sponsor within 24 hours of the investigator becoming aware of the event. The Investigator will report the event to the IRB as per IRB requirements (by fax, mail/delivery, phone, or email). All fatal or life threatening events will be reported immediately to the IRB.

Significant and Non-Significant Adverse Events will be reported to the sponsor as soon as possible, but no later than 5 working days after the occurrence.

Reporting/notification of all adverse events will be made to **Clinical Operations, CooperVision**

[REDACTED]

[REDACTED]

[REDACTED]

[REDACTED]

[REDACTED]

[REDACTED]

[REDACTED]

9.4 DISCONTINUATION FROM THE STUDY

A participant's study participation may be discontinued at any time if, in the opinion of the sponsor or the investigator it is in the best interest of the participant. All discontinuations will be fully documented on the appropriate study forms and the Discontinuation Form will be completed.

Participants discontinued from a study will be reimbursed \$20 per hour for their active involvement in the study (including the initial screening visit).

- The list of possible reasons for discontinuation from the study: Screening failure:
Participants will be discontinued if they do not meet the inclusion and exclusion criteria outlined in section 7.3.
- Unacceptable performance with products to be used in study: Participants may be discontinued if they are unable to achieve acceptable comfort and /or vision and/ or fit with the study products.
- Positive slit lamp finding: Participants may be temporarily or permanently discontinued from the study depending on the severity of the condition and on the judgement of the investigator.
- Adverse event: If a participant experiences an adverse event during the study they may be discontinued based on the clinical judgement of the investigator.
- Symptoms: If the participant has persistent symptoms they may be discontinued based on the clinical judgement of the investigator.
- Disinterest, relocation or illness: The participant may choose to discontinue due to reasons within or beyond their control.
- Violation of protocol or non-compliance: The participant will be discontinued if they are unable or unwilling to follow the protocol specified visit schedules and/or study procedures.
- Instillation of topical ocular medication: The participant will be discontinued if they elect to use a topical ocular medication during the study unless that topical ocular medication is prescribed for a limited duration (less than two weeks) to treat a transient condition; in this case the participant may remain an active participant (at the discretion of the investigator) after stopping topical ocular medication following resolution of the ocular condition).
- Lost to follow-up: The participant will be discontinued if they cannot be contacted and do not return for a final exit visit, and if the investigator has made a reasonable effort to contact the participant for a final study visit.

- Premature termination of the study by the sponsor, the CCLR or the Office of Research Ethics at the University of Waterloo.

A discontinuation form (Appendix 8) will be completed, which requires the signatures of both the participant and the investigator except where the participant is lost to follow-up in which case only the signature of the investigator is required.

10 DEVICE MALFUNCTIONS

A device malfunction means the failure of the device to meet its performance specification or otherwise perform as intended. *Any defective lens that is likely to cause or contribute to a Serious Adverse Event should be reported to the Principal Investigator and the sponsor within 24 hours of the investigator becoming aware of the malfunction.*

Other defective lenses should be reported to the Sponsor as soon as possible (usually in weekly study updates to the Sponsor).

This clinical study will also ascertain satisfaction or preference with subjective attributes such as comfort, vision, or lens handling. Responses to these subjective questionnaires will not be considered as complaints or device malfunctions.

11 STATISTICAL ANALYSIS

11.1 SAMPLE SIZE

Approximately 40 participants will be dispensed in order to target a total of approximately 30 participants completing the study. [REDACTED]

[REDACTED]

[REDACTED]

[REDACTED]

[REDACTED]

[REDACTED]

[REDACTED]	[REDACTED]	[REDACTED]	[REDACTED]
[REDACTED]	[REDACTED]	[REDACTED]	[REDACTED]
[REDACTED]	[REDACTED]	[REDACTED]	[REDACTED]

11.3 STATISTICAL ANALYSIS

All data will be analyzed by the CCLR at the University of Waterloo. Summary statistics will be produced (e.g. mean, standard deviation). Data analysis will be conducted using Statistica, SPSS or SAS. Descriptive statistics will be provided on information regarding baseline variables (age, gender, refractive error distribution, etc.), and follow up visits (e.g. mean, SD). Analysis of variables will be conducted separately on each eye, and data will not be pooled. For assessments conducted for each eye separately, the right eye will be used for analysis if there is no difference between eyes. If a general difference is found (e.g. for paired t-test / Wilcoxon matched pairs) between OD and OS, a comment will be provided.

A Binomial test will be used to analyze the results for the count data of subjective preferences. The number of “no preference” will be evenly distributed to the two options on the basis they would be equally likely to choose either.

[REDACTED]	[REDACTED]	[REDACTED]

The critical alpha level for statistical significance will be set at $p \leq 0.05$, with no adjustments for multiple comparisons.

All participants who were evaluated will be used in the analysis. In the event of missing data, individual data points may be excluded in the analysis and not extrapolated from the collected data.

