3 STUDY DESIGN

This will be a, prospective, double-masked, randomized, bilateral, 1 week cross-over, dispensing study comparing the Invigor IA (test) lens against the Invigor IB (i.e. Select 1 Day) (control) lens. Each participant will be randomized to wear either the test or control as a matched pair first. Both test and control lenses will be used in a daily disposable lens wear modality for one (1) week. It is anticipated that this study will involve 3 scheduled visits:

- Visit 1: Enrollment/ Screening/ Baseline/Fitting/Dispensing of lens pair #1 (either test or control lens);
- Visit 2: 1-week follow-up visit for lens pair #1, and dispensing visit of lens pair #2 (either test or control lens) 6-10 days after lens pair #1 dispense;
- Visit 3: 1-week follow-up visit for lens pair #2 (6-10 days after lens pair #2 dispense) and exit.

The study design is shown in Figure 1.

[figure not shown]

Figure 1: Study design

Each participant will be randomized to wear either the test or control as a matched pair first. Both test and control lenses will be used in a daily disposable lens wear modality.

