- The lens fit will be assessed for fit acceptance (acceptable or not acceptable) and absence of lens defects. If the fit is acceptable and there are no defects, the participant will be allowed to sit for 10 minutes to allow for the lenses to settle.
- Monocular over refraction will be done to determine if a different power is needed.

[REDACTED]

[REDACTED]

[REDACTED]

- Change lens prescription to that noted by over-refraction, if needed. Repeat subjective ratings after lens settling.

- Monocular and binocular logMAR visual acuity (4M) will be recorded with high contrast letters under high and low room illumination*.

[REDACTED]

[REDACTED]

- Lens fitting assessment, according to the guidelines in Appendix 3.
- Monocular lens surface and fit will then be assessed and graded according to the CVI grading scales (Appendix 5).

[REDACTED]

- The participant will be instructed to wear the study lenses for at least 8 hours, and 5 days per week.
- Participants will be provided contact lenses for wear till the next scheduled visit.

- At end of visit the participant will be reminded to return for the next scheduled visit of the first pair.

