7.5.2 VISIT 2: ASSESSMENT OF PAIR #1 AND DISPENSING PAIR #2

This visit will occur 6-10 days after dispense of lens pair #1.

Participants will be asked to wear lenses for **at least two hours** prior to the visit appointment.

Participants who attend without wearing lenses for the specified period will be rescheduled.

- The participant will be asked to score their subjective response as detailed in CVI Grading scales (Appendix 18D).
- The following will be recorded at the one week visit.
 - Hours of lens wear prior to the appointment

[REDACTED]
[REDACTED]

- Binocular comfort at insertion, during the day, end of the day, during the last week
- Overall comfort (0-100 scale), during the last week

[REDACTED]
[REDACTED]

- Binocular vision quality / clarity of vision during the last week (0-100 scale)
- Binocular vision quality / clarity of vision at night during the last week if applicable (0-100 scale)

[REDACTED]
[REDACTED]
[REDACTED]

- Comments by participants

- Unscheduled lens replacements (Y/N) OD and / or OS
- Monocular and binocular logMAR visual acuity (4M) will be recorded with high contrast letters under high and low room illumination.
- Monocular lens surface and fit will then be assessed and graded according to the CVI grading scales. [REDACTED]

- The lenses will be removed and retained in the CCLR (see Section 7.4.6 for disposing consumables).
- Slit lamp biomicroscopy will be assessed according to the approved study biomicroscopy CRF (Appendix 4).
- There will be a break before insertion of pair 2 (of 10 minutes).
- The same procedures will be followed for pair 2 as mentioned in section 7.5.1.
- The contact lenses will be dispensed by a research assistant / study coordinator / technician (in a manner which does not unmask the participant and investigator).
- The lenses will be inserted by the participant from the blister pack as described in Section 7.4.3.

Procedures of lens assessment and dispense will be repeated as detailed in section 7.5.1 for Baseline visit / Dispensing Pair #1.

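### When the two eyes agree the plan compares the lenses on the right eye alone; averaging both eyes per participant would give tighter per-eye comparisons at no cost

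*Combined protocol and SAP*

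**What the plan says.** Section 11.3 handles two-eye data in three consecutive sentences. The first is "Analysis of variables will be conducted separately on each eye, and data will not be pooled". The second says that, for eye-by-eye assessments, "the right eye will be used for analysis if there is no difference between eyes". The third covers disagreement: if a general difference is found "between OD and OS, a comment will be provided". Paired t and Wilcoxon tests are named as examples of how to look for one.

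The design makes both eyes informative about the same contrast. Section 3 states: "Each participant will be randomized to wear either the test or control as a matched pair first". Section 7.5.2 states: "Monocular and binocular logMAR visual acuity (4M) will be recorded with high contrast letters under high and low room illumination". Section 7.5.1 states: "Monocular lens surface and fit will then be assessed and graded according to the CVI grading scales", and section 7.5.2 repeats that assessment at follow-up. Section 2 lists vision (including logMAR) and anterior ocular health (corneal and conjunctival staining) among the primary variables. Lens surface and fit are not among those that can be read. Sections 7.3 and 11.1 target about 30 completers.

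**The concern.** In a cross-over with matched-pair wear, each participant gives two estimates of the same lens difference, one per eye. When the eyes do not differ, section 11.3 keeps one estimate and leaves the other out. That is the situation in which averaging them is easiest to justify. The measurements will already have been made, and with about 30 completers any free precision is worth having.

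The variables at stake are monocular logMAR, lens surface and lens fit, plus staining if the Appendix 4 form grades it per eye.

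**Working it through.** **The plan's own figure.** Section 11.1 gives about 40 dispensed and about 30 completing. The rest of that section is redacted, so no effect size, SD or power is visible and there is no power calculation to reproduce.

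**Inputs.** n = 30 (sections 7.3 and 11.1); alpha 0.05 (section 11.3), taken as two-sided because sidedness is not stated; a paired t comparison (assumed); the correlation ρ between the right-eye and left-eye lens differences (assumed, shown as a range because the documents give none); equal SD of the lens difference in the two eyes (assumed).

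**Variance.** Let D_R and D_L be one participant's test-minus-control difference in each eye, both with standard deviation SD. Then

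Var[(D_R + D_L)/2] = SD² × (1 + ρ)/2,

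so the standard error and interval width, relative to the right eye alone, are multiplied by √((1 + ρ)/2). The number of completers who would give the same precision on one eye is 30 ÷ ((1 + ρ)/2).

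**Right eye alone.** The 95% half-width is t(0.975, 29)/√30 = 2.045/5.477 = 0.373 SD. From the noncentral t distribution, the difference detectable with 80% power is 0.529 SD, a noncentrality of 0.529 × 5.477 = 2.90.

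**Two-eye mean, same 30 participants, same true difference (0.529 SD).** The noncentrality becomes 2.90 ÷ √((1 + ρ)/2).

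| ρ (assumed) | Variance ratio | Interval ratio | Intervals narrower by | Equivalent one-eye n | Detectable at 80% power | Power at 0.529 SD |
|---|---|---|---|---|---|---|
| 0.5 | 0.75 | 0.866 | 13% | 40.0 | 0.458 SD | 89.9% |
| 0.7 | 0.85 | 0.922 | 8% | 35.3 | 0.488 SD | 86.0% |
| 0.8 | 0.90 | 0.949 | 5% | 33.3 | 0.502 SD | 84.0% |
| 0.9 | 0.95 | 0.975 | 3% | 31.6 | 0.516 SD | 82.0% |
| 1.0 | 1.00 | 1.000 | 0 | 30.0 | 0.529 SD | 80.0% |

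Under equal SDs the gain disappears only at ρ = 1. The mean stays one value per participant, so n remains 30. Treating 60 eyes as independent would ignore the correlation and is not what is proposed.

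**The case against.** **Right-eye analysis is accepted practice and valid.** This stands. One eye per participant avoids false replication, and nothing here suggests bias.

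**The gain may be small.** This stands too. At correlations of 0.8 to 0.9 the intervals narrow by only 3% to 5%. The case rests on the cost being nil.

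**Much of the primary comparison is untouched.** Binocular logMAR, binocular ratings, preference and discontinuation do not depend on this rule, and descriptive statistics for follow-up are not limited to one eye. That confines the point to the per-eye comparisons.

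**Redacted text may say more.** Parts of sections 11.1 and 11.3 are blacked out and section 11.2 is not visible. Variable-specific methods could be there.

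Four stronger readings are tempting, and the documents do not support them:

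- *Section 11.3 contradicts itself.* The three sentences can be read as one procedure: eyes are not pooled, the right eye is the default, and separate eye results with a comment are given if the eyes differ. The wording is loose, but contradiction is not the only reading.
- *Chance OD/OS differences will often divert the analysis.* Significance is set at 0.05 "with no adjustments for multiple comparisons", which invites a false-trigger calculation. But the text does not say which variables, lenses or visits are tested between eyes, so any count of tests would be invented.
- *Left-eye safety findings are lost.* Section 9.1 defines an adverse event as "any undesirable clinical occurrence in a participant, whether it is considered to be device-related or not", without regard to eye. Only the lens comparison is affected.
- *Staining should use the worse eye.* That changes the quantity estimated and is not reliably more powerful. A simulation used 30 participants, presence/absence staining at 80% per-eye prevalence, a latent lens shift of 0.5 SD, a latent inter-eye correlation of the lens difference of 0.5, and a Wilcoxon signed-rank test; all of these but the 30 are assumptions. Worse-eye power was about 15%, against about 26% for the right eye. The two-eye mean stayed above the right eye in every scenario run.

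**Conclusion.** The point holds as a matter of efficiency. When the eyes agree, the right-eye rule leaves already-collected left-eye data out of the lens comparison. A per-participant mean would recover precision equivalent to roughly 2 to 10 extra completers (31.6 to 40.0 against 30) over assumed correlations of 0.9 down to 0.5.

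This rests on the assumed correlation, on similar variability in the two eyes, on 30 completers and, for staining, on per-eye grading. It does not show that the planned analysis is invalid or that its conclusions would change. It is a free improvement.

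**What to change.** Replace the right-eye rule, and the OD/OS test that decides whether it applies, with one rule:

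> Variables recorded for each eye will be analysed as the mean of OD and OS per participant and lens, with the participant as the unit of analysis (eyes are not treated as independent). OD and OS will also be tabulated by lens; any OD/OS difference will be described and will not change the analysis.

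The sentence that rules out pooling should be replaced as well, or should state that averaging within a participant is not pooling. If staining is graded per eye, use the same two-eye mean for the comparison; the OD/OS table will show findings isolated to one eye. If the redacted parts already set methods for particular variables, check them against this rule.

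The cost is a change of wording. No measurement, visit or participant is added.

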7.3 Participants

Up to 40 participants will be successfully enrolled and dispensed/randomized with the study products, with a target of 30 participants completing the study. Participants will be recruited using CCLR records and advertising approved by the UW Office of Research Ethics (Appendices 2 &11). Informed consent will be obtained for all participants prior to their enrolment in the study (Appendix 1).

Each participant will be given a unique ID number. Additionally, all participants must meet the study inclusion and none of the exclusion criteria listed below.

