7.4 STUDY MATERIALS

7.4.1 CONTACT LENS

Participants will be randomized to receive either the test or control lens as a matched pair at each visit per a predetermined randomization schedule (Appendix 14). The lenses (test and control) will be labelled as Invigor IA (test) and Invigor IB (control).

The Invigor IA (test) lens is an investigational product and will be subject to pre-clinical assessment before being released for the study. This lens is not commercially available in Canada and therefore an ITA (investigational testing authority) from Health Canada has been received.

The Invigor IB (control) i.e. Select 1 Day lens is approved by FDA and Health Canada, and is commercially available in Canada and the USA, however for the purpose of this study, it has been labelled as Invigor IB and is covered under an ITA issued by Health Canada.

Details of the Invigor IA (test) and Invigor IB (control) study lenses used in this study are shown in Table 1. The test lens is the Invigor IA (test) lens and approved by Health Canada for use in the study.

Table 1: Study lenses used in this study

	Invigor IA (test)	Invigor IB (control) (i.e. Select 1 Day)
Manufacturer	CooperVision	CooperVision
HC License No.	-	81009
Material	somofilcon A	somofilcon A
Health Canada license #	-	81009
EWC (%)	56%	56%
Dk/t (-3.00D)	86.0	86.0
BOZR (mm)	8.6	8.6
Diameter (mm)	14.0	14.0
Sphere power (D)	-1.00 to -6.00 (0.25 steps)	-1.00 to -6.00 (0.25 steps)

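### Splitting no-preference answers evenly before a binomial test on everyone makes the preference test too conservative once about 30% or more have no preference

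*Combined protocol and SAP*

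**What the plan says.** Section 2 lists preference, together with comfort, among the primary variables of interest. At Visit 3 (section 7.5.3) three answers are offered: "Participant will also rate their overall preference between lens pair #1, lens pair-#2 or no preference". The readable items are "Overall comfort preference, and reason for preference" and "Overall vision preference, and reason for preference".

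Section 11.3 states: "A Binomial test will be used to analyze the results for the count data of subjective preferences". It then says that the no-preference answers "will be evenly distributed to the two options on the basis they would be equally likely to choose either". The significance level is p ≤ 0.05 without multiplicity adjustment, and "All participants who were evaluated will be used in the analysis". The binomial denominator is therefore all respondents, including those who chose neither lens.

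The readable text does not say whether the test is one- or two-sided, or what happens to the leftover answer when the number of ties is odd. It gives no expected rate of no-preference answers. Part of 11.3 and the sample-size rationale are redacted, and nothing below depends on what they may contain.

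**The concern.** The plan's justification describes a random choice: someone with no preference would pick either lens with equal probability. The rule it adopts is a fixed allocation, which has no randomness. A binomial test on the resulting counts charges each tied participant the variance of a coin toss that never took place. The difference between the lenses is unchanged by the split, but it is judged against too large a standard error, increasingly so as ties rise.

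Ties could well be common here. Table 1 in section 7.4.1 gives both lenses the same material, water content, Dk/t, base curve and diameter. That says nothing about how strongly those who do choose would lean.

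The hypothesis in section 2.1 is that the test lens performs at least as well as the control. A missed preference for the test lens loses evidence of superiority. A missed preference for the control could be misread as evidence of equality. The 0–100 ratings, visual acuity and slit-lamp measures are not affected.

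**Working it through.** **Inputs.** From the documents: n = 30 completers (section 7.3, "with a target of 30 participants completing the study") and n = 40 as the enrolment ceiling; p ≤ 0.05; ties split evenly with all respondents in the denominator (11.3). Assumed: two-sided exact binomial test; tie rate t from 0 to 50%; lean among choosers 50:50 for size, and 70:30 or 80:20 for power. The readable text gives no power or effect size, so there is no figure of the plan's to reproduce.

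**Mechanism.** Let A and B be the numbers choosing each lens and T = n − A − B the ties.
- The split count is A + T/2. Given T and the null, A ~ Binomial(n − T, ½), so its variance is (n − T)/4. The test uses n/4.
- In z form the split test is (A − B)/√n and the sign test is (A − B)/√(n − T). For 15 v 5 with 10 ties: 10/√30 = 1.83 against 10/√20 = 2.24.
- The null variance is too large by a factor 1/(1 − t). In large samples a nominal 5% test then has true size of about 1.9%, 1.1% and 0.6% at t = 30%, 40% and 50%.

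**Counts needed, with no assumption about lean.** At n = 30 the split test needs 21 of 30 (20/30 gives p = 0.0987; 21/30 gives p = 0.0428).

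| Ties | Choosers | Split test needs | Sign test needs |
|---|---|---|---|
| 0–8 (even) | 30–22 | same | same |
| 9 | 21 | 16 or 17* | 16 |
| 10 | 20 | 16 | 15 |
| 12 | 18 | 15 | 14 |
| 14 | 16 | 14 | 13 |
| 16 | 14 | 13 | 12 |
| 18 | 12 | 12 | 10 |
| 20 | 10 | impossible | 9 |

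*Depends on where the odd leftover goes.

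The hard limit: with 20 ties, ten unanimous choosers give 10 + 10 = 20, below 21. With 21 ties, 9 + 11 = 20 at best. At n = 40 the split test needs 27 (26/40 gives p = 0.0807; 27/40 gives p = 0.0385), and with 28 ties the most it can reach is 12 + 14 = 26.

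Examples at n = 30, split v sign test:
- 15 v 5, 10 ties: 0.099 v 0.041
- 13 v 3, 14 ties: 0.099 v 0.021
- 11 v 1, 18 ties: 0.099 v 0.006
- 10 v 0, 20 ties: 0.099 v 0.002

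**Size and power at n = 30.** Exact enumeration with T ~ Binomial(n, t) and A given T ~ Binomial(n − T, lean). Split-test ranges run from giving an odd leftover to the smaller side to giving it to the larger side. Each cell is split v sign test, in %.

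| Tie rate | True size | Power, 80:20 | Power, 70:30 |
|---|---|---|---|
| 10% | 2.6–4.2 v 2.9 | 86–90 v 88 | 45–53 v 47 |
| 20% | 1.8–3.1 v 3.0 | 76–83 v 83 | 35–43 v 42 |
| 30% | 1.1–2.1 v 2.9 | 62–71 v 77 | 24–32 v 37 |
| 40% | 0.6–1.3 v 3.0 | 43–54 v 69 | 14–21 v 32 |
| 50% | 0.3–0.6 v 2.8 | 24–34 v 59 | 7–11 v 26 |

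At 25% ties there is already a small loss under every leftover rule: at most 77.4% v 79.8% at 80:20, and 37.5% v 39.5% at 70:30. At n = 40 the same is seen at 20% ties (at most 91.6% v 93.0% at 80:20). At n = 40, 40% ties and 80:20, power is 59–67% v 83%.

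**Sensitivity to sidedness.** With a one-sided 0.05 test, n = 30, 30% ties and a random leftover, size is 2.5% v 3.3%, and power at 75:25 is 64.6% v 70.5%. The direction is the same.

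**Exception.** With an even number of ties the split p-value is never below the sign-test p-value (checked for n = 25–40, all counts). With an odd number, giving the leftover to the larger side can make the split test slightly more liberal. At n = 30 only two tables reject under that rule but not under the sign test: 20 v 9 with 1 tie (0.043 v 0.061) and 19 v 8 with 3 ties (0.043 v 0.052).

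**The case against.** The strongest reply is that the harm is conditional. No tie rate is given, and near-identical lenses may produce many ties but give no reason to expect an 80:20 lean, where the absolute losses are largest. Around 30% ties the rejection threshold moves by one participant or none, and the most striking examples need 60–67% ties. At 70:30 and 30% ties power is poor either way (24–32% v 37%), so the sample size is the main limit. The sign test is conservative too, with true size of 2.8–3.0%, and with few ties it may be marginally less powerful than the split. The error also does not create false claims of preference, apart from the two odd-tie tables above, and comfort and vision are separately rated on 0–100 scales.

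All of that is correct, and it limits the size of the point. It does not rescue the rule. One participant in the critical count at 10 ties decides a result such as 15 v 5. Discreteness affects both tests, so it does not explain why the size of the split test falls to 0.3–0.6% at 50% ties while the sign test stays near 3%. An analysis rule for a primary variable should not lose its ability to reject within a plausible range of data. Redacted text might add a further analysis, but the splitting sentence is readable and stands as the rule.

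**Conclusion.** The concern holds. Allocating ties by rule and then testing all n as independent 50:50 choices overstates the null variance, and this follows from the written rule alone. The consequence depends on the tie rate, which is unknown: negligible at 10%, small at 20–25%, and material from about 30%. At n = 30 and an 80:20 lean the power loss against a sign test is 6–15 points at 30% ties (77 − 71 to 77 − 62) and 15–26 points at 40% (69 − 54 to 69 − 43). From 20 ties rejection is impossible. The effect is symmetric between the lenses and confined to the preference questions. The power figures rest on the assumed tie rates and leans and a two-sided test; the critical counts need only n = 30 and a two-sided test. This should be corrected, but it does not undermine the other primary variables.

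**What to change.** Replace the splitting sentence in section 11.3 with wording such as: *Preference will be tested with an exact two-sided binomial (sign) test among participants who state a preference. The numbers preferring test, control and neither will be tabulated, and net preference (test minus control) in all participants will be given with a 95% confidence interval using the multinomial variance.* The even split could stay as a sensitivity analysis if the odd-leftover rule is stated.

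The first sentence and the table cure the defect; the interval is a useful secondary addition. An adjusted Wald interval (add 1 to each preference count, use n + 2) is adequate. At n = 30 with 0–50% ties its coverage is 93.0–95.7% for leans of 50:50, 70:30 and 80:20, and it reaches 96.2% at 60:40 without ties and at 90:10 with 30% ties. For 3 test, 13 control and 14 neither, net preference is −10/30 = −0.33, and the adjusted interval is −0.55 to −0.08, centred at −10/32 = −0.31. A non-significant result from either test should not be read as showing that the lenses are equally preferred.

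The cost is two sentences of analysis text, since all three answers are already collected at Visit 3. The downsides are modest. The sign test uses only choosers, so the no-preference share must be shown beside it. It cannot reach p ≤ 0.05 with fewer than 6 choosers (2 × 0.5⁵ = 0.0625), that is, with 25 or more ties of 30. The interval is wide: at zero net preference and n = 30 its half-width is about 0.33 at 10% ties and 0.25 at 50%.
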